### 9.9. Genetic data

Each of the following genes will be tested: SOD1, C9orf72, FUS and TARDBP. Where applicable, detailed information about the mutation (e. g. expansion, expansion number, substitution and location, deletion/duplication and location) will be collected along with an assessment of pathogenicity as adjudicated by the laboratory (e. g. benign, likely benign, likely pathogenic, pathogenic, variant of uncertain significance).

*Table 10: Description of the genes and respective mutation type*

Gene	Variant	Mutation type	Interpretation and classification
SOD1	Y/N	Substitution Deletion Insertion Duplication Inversion	Benign Likely Benign Likely Pathogenic Pathogenic Variant of Uncertain Significance
C9orf72	Y/N	Expansion	Benign Pathogenic
FUS	Y/N	Substitution Deletion Insertion Duplication Inversion	Benign Likely Benign Likely Pathogenic Pathogenic Variant of Uncertain Significance
TARDBP	Y/N	Substitution Deletion Insertion Duplication Inversion	Benign Likely Benign Likely Pathogenic Pathogenic Variant of Uncertain Significance

## **10. Quality assurance**

### **10.1. Data quality**

During and/or after completion of the registry, quality assurance officers named by APST or the regulatory authorities may wish to perform onsite audits. The Investigator will be expected to cooperate with any audit and to provide assistance and documentation (including source data) as requested. Data quality is facilitated on a web-based secure clinical research software (studioMED+, Germany) that encompasses a study management component and an electronic case report form (eCRF). It digitally enables the multi-step workflow of data capture linking all data entry roles at participating ALS centers. At the studioMED+ software, the data from all different data sources are captured and processed.

### **10.2. Review of data**

The study software studioMED+ is used as a data management system in this study and enables the storage and tracking of study data, especially study visits, by means of an electronic case report form (eCRF). StudioMED+ provides study-related documents and an overview of all study patients. Received data will be controlled for completeness using the studioMED+ study software. The reporting tool of the same software will be used to report registry numbers and collected data at regular intervals (monthly).

### **10.3. Genetic review board**

A review board on genetic results will be implemented. The genetic review board will serve as a consulting body for the interpretation of complex or uncertain genetic research results. This refers mostly to result in the categories "likely pathogenic and "variant of uncertain significance" (details in 9.9). The genetic review board comprises of the following members:

- [name]. [name], Mannheim University Hospital, certified neurologist and expert in ALS genetics
- [name]. [name], Charité – Universitätsmedizin Berlin, certified geneticist, expert in genetic consulting
- PD [name] [name], Charité – Universitätsmedizin Berlin, certified neurologist and expert in neurogenetic consulting

## **11. Statistical methods and analysis plan**

Descriptive statistics will be presented for each assessment of all subjects at study visit. Subgroup analyses by genetic or clinical criteria or other baseline characteristics will be performed. Secondary endpoints in the genetically defined subsets of ALS with confirmed SOD1 or C9orf72 mutations will be compared to genetically tested patients with ALS not revealing any ALS-associated mutation in any of the tested genes. Descriptive statistics will be used for the statistical analysis (frequency in percentage, mean, median, standard deviation in  $\pm$ , interquartile ranges (Q1, Q3), and ranges (min, max). The standardized mean difference (SMD) will be applied in this study. The SMD of each measure over up to 12 months will be estimated using the change in measure between each subject's assessments and within each individual. The standardized mean difference expresses the size of intervention effect. Difference of frequencies between two groups will be assessed by Fisher's exact test or Chi-square test, or within metric data by using the Shapiro-Wilk test, Kruskal-Wallis test and Mann-Whitney U-test. The Wilcoxon test will be employed for the analysis of statistical power of ordinal-scaled data, while metric data were subjected to the t-test (ALS-FRS, MYMOP). This analysis applies to the comparison of genetically defined subsets of ALS (baseline characteristics and changes over time). The analysis of follow-up data is limited to complete

cases, since not all patients are expected to complete end-of-study assessments due to disease progression, e.g., death. It is aimed to compare the baseline characteristics and the proportion of death between those who completed and not those not completed 6 months and 12-month assessment. Statistical significance will be ascertained by according to an error risk of up to 5% (p-value < 0.05). Associations for the clinical outcomes will be assessed by linear regression models adjusted for potential confounding factors. Results of the longitudinal observations will be also controlled for the influence of any covariate (sex, age, intervention history). Longitudinal analysis by means of group comparisons will be applied by using a multivariate analysis. 95% confidence intervals with p-values will be reported. In order to draw conclusions from the samples with censored data, missing data records will be omitted and treated as missing values. Data analysis will be performed using SPSS (Version 25.0).

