## 1. Visit schedule

Table 1: Visit schedule

Visit schedule	V1 M1-M3 (Baseline)	V2 M4-M8* (Follow-Up)	V3 M9-M14 (Closure)
Demographic data			
Age	x		
Gender	x		
Place of residence	x		
Social characteristics			
Employment status	x		
Marital status	x		
Education level	x		
Living arrangement	x		
Disease history			
Date of disease onset	x		
Date of initial diagnosis	x		
Age at disease onset	x		
Duration of disease	x		
Date of death (if applicable)			
Family history			
Family members who are living with ALS	x		
Family members who died of ALS	x		
Family members who are living with FTD	x		
Family members who died of FTD	x		
Family members who are suffering from neurological/psychiatric disorder	x		
Family members who died of any neurological/psychiatric disorder	x		
Clinical classification			
ALS subtypes	x		
Region of onset	x		
Functional deficits and progression			
ALS Functional Rating Scale (ALS-FRS)	x	x(2)	x
ALS progression rate (loss of ALS-FRS per month)	x	x(2)	x
King's classification of clinical stages of ALS	x		x
Serum neurofilament light chain (sNFL)	x	x(2)	X(2)
Interventions and health care measures			
Use of PEG	x		x
Use of non-invasive ventilation	x		x

Use of tracheotomy	x		x
Provision of a manual wheelchair (1)	x		
Provision of complex power wheelchair (1)	x		
Provision of a communication device (1)	x		
Provision of assistive technology (1)	x		
Physical, occupational and speech therapy (1)	x		
Riluzol and symptomatic pharmacotherapy (1)	x		
Treatment expectation			
MYMOP2, measure yourself outcome profile	x	x(2)	x(2)
Molecular genetic analysis			
C9orf72	x		
FUS	x		
SOD1	x		
TARDP	x		

M: month, V: visit; 1 = subgroup of users of APST management platform, 2 = in subgroup of patients with SOD1 mutation data will be collected more frequently (up to monthly collection of existing data of sNfL; up to weekly self-assessment of ALS-FRS using the ALS-App in addition to on-site assessment of ALSFRS-R during site visits). In the main cohort of non-SOD1 patients the collection of sNfL data is limited to the visits V1 (baseline) and V2 (follow-up).

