## **4. Overall study design**

### **4.1. Study design**

This is a longitudinal, non-interventional, non-randomized, multicenter, prospective study conducted in subjects with ALS. Duration of study participation for each subject will be up to approximately 12 months. Subjects will be enrolled to receive questionnaires, in order to assess the variables and to provide blood samples for molecular genetic testing. Approximately 1,000 subjects are planned to complete the study. It is anticipated that up to approximately 18 sites will be activated in Germany. This registry study will be reported according to STRO-BE-statement.

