### **4.3. Overall study duration and assessments**

The study will include ALS patients at specialized outpatient clinics (study sites). All subjects will undergo 3 assessments over a period of approximately 12 months. The assessment schedule will be as follows:

- Assessment at baseline: initial assessment of subjects including blood sampling and molecular genetic analysis
- Assessment at follow-up: follow-up assessment that is realized in a 6-month interval
- Assessment at the end of the study: final assessment after 10 to 14 months interval and optional

  

- Assessment for interim analysis: interim analyses performed for this study at variable time points, at least after all subjects complete the 6-month assessments.

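### Genotype comparisons of change over time do not account for elapsed time, although the visit windows let the interval between assessments vary widely

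*Combined protocol and SAP*

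**What the plan says.** Section 11 states: "The SMD of each measure over up to 12 months will be estimated using the change in measure" from one of a subject's assessments to another. It adds that the tests apply to comparisons of genetically defined subsets, both at baseline and for changes over time, with a t-test for ALS-FRS and MYMOP. It also plans linear regression adjusted for confounders, control for sex, age and intervention history, and a multivariate longitudinal analysis that is not specified further. Elapsed time, visit date and a time term are not mentioned.

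Visit timing appears in two places.

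- Table 1 (section 1) has columns that begin "V1 M1-M3 (Baseline", "V2 M4-M8* (Follow-Up" and "V3 M9-M14 (Closure". No minimum gap between visits is given.
- Section 4.3 puts the follow-up visit at a 6-month interval and describes the last visit as "final assessment after 10 to 14 months interval".

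Section 9.6.2 defines a monthly progression rate as (48 - score) divided by months since diagnosis.

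**The concern.** ALS-FRS falls over time, so the difference between two assessments depends on how fast the patient declines and on how far apart the assessments are. An analysis of the plain difference mixes the two. Two patients with identical decline get different change scores if one is seen early in the V3 window and the other late.

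Two consequences follow. If timing is unrelated to genotype, the varying interval inflates the SD of change and pulls the standardised difference towards zero. If timing is related to genotype, it produces a difference between SOD1 or C9orf72 carriers and mutation-negative patients that is not a difference in progression. The comparison of these groups on progression is a named objective (section 3.3).

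**Working it through.** The plan gives no power, SD or effect size for these comparisons, so there is no planned figure to reproduce. Windows come from Table 1 and section 4.3. Slopes, SDs and the distribution of visits within windows are assumptions.

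**1. Range of elapsed time.** Minimum = first month of the later window minus last month of V1. Maximum = last month of the later window minus first month of V1.

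- V1-V2: 4 - 3 = 1 month to 8 - 1 = 7 months (7-fold).
- V1-V3: 9 - 3 = 6 months to 14 - 1 = 13 months (2.2-fold).
- V1-V3 on section 4.3 alone: 10 to 14 months (1.4-fold). Satisfying both sections: 10 to 13 months (1.3-fold).

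**2. Typical spread.** With visits uniform and independent within their Table 1 windows, the variance of each visit time is width²/12.

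- V1-V2: mean 6 - 2 = 4.0 months; variance 2²/12 + 4²/12 = 1.67; SD 1.3.
- V1-V3: mean 11.5 - 2 = 9.5 months; variance 2²/12 + 5²/12 = 2.42; SD 1.6.
- Section 4.3, uniform over 10 to 14 months: mean 12; variance 4²/12 = 1.33.

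**3. Noise when timing is unrelated to genotype.** For slope mean m and SD s, and elapsed time with mean μ and variance v, Var(change) = s²(μ² + v) + m²v. With a fixed interval, SD = sμ. Take m = 1 and s = 0.6 points per month, without measurement error.

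| Interval | Var(change) | SD | SD at fixed interval | Increase |
|---|---|---|---|---|
| V1-V3, Table 1 | 0.36 × (90.25 + 2.42) + 2.42 = 35.8 | 5.98 | 5.70 | 5% |
| V1-V3, section 4.3 | 0.36 × (144 + 1.33) + 1.33 = 53.7 | 7.33 | 7.20 | under 2% |
| V1-V2, Table 1 | 0.36 × (16 + 1.67) + 1.67 = 8.03 | 2.83 | 2.40 | 18% |

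Measurement error shrinks these percentages. A simulation with slope SD 0.7, measurement SD 2 per visit and a true slope difference of 0.3 points per month gave these standardised differences:

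- V1-V3: 0.38 with variable timing against 0.39 with fixed timing.
- V1-V2: 0.27 against 0.30.

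**4. Bias if timing differs by genotype.** False difference = slope × difference in mean elapsed time. At 0.5 to 1.5 points per month this is 0.5 to 1.5 points for each month. In the same simulation setting (slope mean 1, equal in both groups), the SD of change is 4.29 for V1-V2 and 7.46 for V1-V3. A 1-month difference then gives a spurious SMD of 1/4.29 = 0.23 or 1/7.46 = 0.13.

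**5. Whether the 9.6.2 rate helps.** Take a patient 12 months after diagnosis who has lost 12 points from 48 and then loses 1.5 points per month. At V3 the formula gives (12 + 9)/18 = 1.17 if V3 is 6 months later, and (12 + 19.5)/25 = 1.26 if it is 13 months later. The between-visit slope is 1.5 in both cases. The rate does not recover it, itself shifts with timing, and does not cover MYMOP or sNfL.

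**The case against.** The strongest reply is that the effect is small. The 7-fold and 2.2-fold ranges are window extremes, and typical gaps vary much less. On section 4.3 the V1-V3 range is only 1.4-fold, and timing unrelated to genotype barely moves the V1-V3 standardised difference. The unspecified regression and multivariate analyses do not exclude a time term. The study is described as exploratory, and its primary endpoint is variant frequency. All of this stands and limits the weight of the point. It does not supply a time term, and the effect on V1-V2 is larger.

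Two stronger readings are tempting, and the documents do not support them.

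- A reader might infer that a spurious SOD1 difference is likely because SOD1 carriers are assessed more often. The Table 1 footnote adds app self-ratings on top of site visits and more frequent collection of existing sNfL values. It does not say that V1, V2 or V3 fall at different times in carriers, and it says nothing about C9orf72. A route to bias remains open, because section 11 does not say which assessments define the change.
- A reader might count "Duration of study participation for each subject will be up to approximately 12 months" (section 4.1) as a third statement of the V3 window. It gives the length of participation, not a visit window.

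Dividing each change by its elapsed months is also a poor remedy. With a measurement SD of 2 per visit, the error SD of such a rate is 2√2/1 = 2.8 points per month at a 1-month gap and 2√2/7 = 0.4 at 7 months.

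**Conclusion.** The point holds as a limited weakness in the longitudinal genotype comparisons. Section 11 describes no adjustment for elapsed time, Table 1 permits widely varying intervals, and the per-month rate in 9.6.2 does not fill the gap.

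For V1-V3, timing unrelated to genotype raises the SD of change by about 5% on Table 1 and by less than 2% on section 4.3. For V1-V2 on Table 1 it is about 18% before measurement error is allowed for. These figures rest on the assumed slopes and on uniform visit timing. Bias of 0.5 to 1.5 points per month of mean timing difference is conditional on timing, or the choice of assessments, differing by genotype. That is possible, not demonstrated. Variant frequency is unaffected.

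Table 1 and section 4.3 also disagree. If section 4.3 counts from baseline, V1-V3 gaps of 6 to 9 months fit Table 1 but not section 4.3. The midpoints of the V1 and V2 windows are 4 months apart, while section 4.3 names 6. This matters because section 11 restricts follow-up analysis to complete cases and compares completers with non-completers of the 6- and 12-month assessments.

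**What to change.** In section 11, for the longitudinal genotype comparisons:

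- Use a mixed model with actual months since V1 and a genotype-by-time term. For ALS-FRS, standardise the difference in slopes instead of the difference in change scores.
- For MYMOP and sNfL, include actual time without requiring a linear course.
- State that the comparison uses the scheduled V1 to V3 assessments in all groups, with the extra SOD1 data reported separately. For sNfL, Table 1 limits non-SOD1 patients to V1 and V2, so those are the common visits.
- Reconcile the visit windows in Table 1 and section 4.3, and define a completer from the result.

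The cost is analysis-plan wording, slightly more analysis work, and an actual assessment date at each visit. Section 10.2 says the study software tracks visits, so what remains is to confirm that the date of each assessment is stored.

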#### **3.3. Additional objectives**

The additional objectives of this study are as follows:

- To investigate the demographic and social characteristics
- To investigate the family history for ALS or FTD
- To investigate the clinical classification, functional deficits, disease progression and health care measures in a subset of ALS patients with pathogenic variants in the genes of SOD1

or C9orf72 as compared to ALS patients with no ALS-associated mutations in the investigated genes

- To register available data on serum concentration of neurofilament light chain (sNfL)
- To register the history of interventions and health care measures including percutaneous endoscopic gastrostomy (PEG) and ventilation therapy
- To register the provision with assistive technology devices, symptomatic pharmacotherapy and physical, occupational and speech therapy
- To identify patient's treatment expectations towards ALS therapy using the Measure Your Medical Outcome Profile (MYMOP2)

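### The only effect size the plan names, an SMD of within-subject change, is called an intervention effect in a study that assigns none, and no between-genotype effect measure is defined

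*Combined protocol and SAP*

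**What the plan says.** Section 11 announces: "The standardized mean difference (SMD) will be applied in this study". For each measure, over up to 12 months, the SMD is to be "estimated using the change in measure between each subject's assessments and within each individual". The interpretation follows at once: "The standardized mean difference expresses the size of intervention effect". The statistical methods entry of the Synopsis lists the SMD as its only method and ends with the same sentence. Neither place says which standard deviation is the divisor.

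On design, Section 4.1 states: "This is a longitudinal, non-interventional, non-randomized, multicenter, prospective study conducted in subjects with ALS". Among the additional objectives, Section 3.3 asks for clinical course and care in patients with pathogenic variants in SOD1 "or C9orf72 as compared to ALS patients with no ALS-associated mutations in the investigated genes".

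Section 11 also commits to this comparison. The SOD1 and C9orf72 subsets "will be compared to genetically tested patients with ALS not revealing any ALS-associated mutation in any of the tested genes". After listing the tests it adds: "This analysis applies to the comparison of genetically defined subsets of ALS (baseline characteristics and changes over time". It then plans linear regression with adjustment for confounders, and continues: "Longitudinal analysis by means of group comparisons will be applied by using a multivariate analysis". Confidence intervals at the 95% level are promised.

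**The concern.** An intervention effect needs a contrast between receiving and not receiving something. The SMD described here has no such contrast: it compares a patient with the same patient some months earlier. In a progressive disease that change is mostly the course of the illness, so the stated interpretation does not fit the quantity.

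Nor does the SMD answer the comparative objective. A reader of the results will want to know how much faster or slower carriers decline than mutation-negative patients. The one effect size the plan names does not give that, and the analyses that do compare genotypes are listed as tests and models without a stated estimate.

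Two things are at stake. A published table could present ordinary decline as an intervention effect. This would be awkward for SOD1 in particular, because Section 12.3.1 describes that gene as currently having therapeutic relevance. Readers could also set the SMDs of two genotype groups side by side and take the gap as a genotype difference, which it need not be.

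**Working it through.** The plan states no target SMD, power or sample size formula, so there is no figure to reproduce. The check compares the text with itself and then uses illustrations. All ALS-FRS means, SDs and correlations below are assumed; none comes from the documents.

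**1. Is there an intervention contrast?** Section 4.1 says no intervention is assigned. Table 8 records gastrostomy, ventilation, devices, therapies and riluzole. Section 11 brings intervention history in only as a covariate. The SMD is defined for every measure between assessments, not before and after a procedure and not users against non-users. So there is no intervention contrast.

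**2. Is there a genotype contrast in the SMD?** Its stated input is within-subject change. No between-group form is given.

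**3. Can within-group SMDs stand in for a genotype contrast?** Suppose the divisor is each group's own SD of change.
- Within-group SMD = mean change / SD of change.
- Between-group SMD = difference in mean change / sqrt((SD1² + SD0²)/2).

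| Assumed change (SD): carriers; negatives | Within-group SMDs | Difference in change | Between-group SMD |
|---|---|---|---|
| -10 (8); -5 (4) | -10/8 = -1.25; -5/4 = -1.25 | -5 | -5/sqrt((64+16)/2) = -0.79 |
| -6 (8); -6 (4) | -6/8 = -0.75; -6/4 = -1.50 | 0 | 0 |

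In the first row a 5-point difference disappears. In the second, equal declines look twofold different.

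**4. Does the missing standardiser matter?** Assume a mean change of -8 and an SD of 8 at both visits. Dividing by the baseline SD gives -8/8 = -1.00. Dividing by the SD of change, sqrt(2 × 8² × (1 - r)), gives -0.85 at visit-to-visit correlation r = 0.3 and -2.24 at r = 0.9. The same data give quite different values.

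**5. How large could natural decline look?** Assume a 12-month loss of 6 to 12 points, a slope SD of 0.6 points per month and a measurement SD of 3.
- Error entering the change once: SD = sqrt((12 × 0.6)² + 3²) = 7.8, and the SMD in absolute value is 6/7.8 = 0.77 to 12/7.8 = 1.54.
- Error entering at each of two visits: SD = sqrt(7.2² + 2 × 3²) = 8.36, and the SMD is 0.72 to 1.44.

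These ranges hold only for these inputs and this divisor.

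**6. What precision would a between-genotype SMD have?** Section 2.1 gives SOD1 frequencies of 14.8% (familial) and 1.2% (sporadic), and C9orf72 frequencies of 34% and 5%, with 6.5% overall. The C9orf72 figures imply a familial share f from 0.34f + 0.05(1 - f) = 0.065, so f = 0.015/0.29 = 5.2%. The same section puts sporadic ALS above 90%, so f = 10% is taken as the upper end. With 1,000 completers (Section 5.1 expects more than that) and carriers as likely to complete as others:
- SOD1: 19 to 26 carriers.
- C9orf72: 65 to 79 carriers.
- Mutation-negative: about 916 to 895, ignoring FUS and TARDBP, for which no frequency is given.

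The 95% half-width near zero is 1.96 × sqrt(1/n1 + 1/n0): 0.45 to 0.39 for SOD1 and 0.25 to 0.23 for C9orf72. The contrast can be estimated, though imprecisely for SOD1, which is a reason to report its interval.

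**The case against.** The strongest reply is that the genotype question is already covered. Section 11 compares carriers with mutation-negative patients, applies its tests to changes over time, and adds adjusted regression, longitudinal group comparisons and confidence intervals. This stands. A reader might infer from the SMD's definition that no genotype comparison is planned; the text contradicts that. What is missing is narrower: a named effect measure for those comparisons. The sentence extending the analysis to genetic subsets could be read to include the SMD, but the SMD would then be computed inside each subset, still with no contrast between them.

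Second, a reader might take the SMD for the study's main or headline statistic. The plan does not rank it. The only primary endpoint is genetic variants, the evaluation is declared exploratory, and a synopsis abbreviates. It is fair to say only that the SMD is the one effect size named and the only method in the Synopsis.

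Third, it is tempting to say that the SMD is mean decline divided by its SD. The documents give no divisor. With a common SD, equal declines would give equal SMDs, so step 3 of the working is conditional and the firm criticism is that the standardiser is unstated.

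Finally, the sentence may be a textbook definition carried over, and the protocol calls itself non-interventional and commits to STROBE reporting. That lowers the risk of harm but does not make the sentence correct. A reader might also suspect that a drug effect is being claimed. Section 11 does not mention gene-targeted medicines, and nothing in it supports that reading.

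**Conclusion.** The point holds as one of interpretation and specification. The description of the SMD as an intervention effect is wrong for this design in both places where it appears, and this rests on the text alone. Also on the text alone, the standardiser is undefined and no between-genotype effect measure is stated for comparisons that are otherwise planned.

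The numerical size is illustrative. The SMD ranges depend on assumed declines and SDs, and the equal-or-different SMD examples also need group-specific SDs of change as divisor. The documents do not support saying that the genotype objective has no analysis or that the registry's principal result is affected. It should be corrected before results are reported, but it does not threaten the study.

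**What to change.** 1. Delete the intervention-effect sentence in the Synopsis and in Section 11.
2. For the genotype comparisons already planned, name the estimate: carrier minus mutation-negative difference in change, separately for SOD1 and C9orf72, with a 95% confidence interval. For ALS-FRS express it per month between study assessments. The Table 1 windows (V1 in months 1 to 3, V3 in months 9 to 14) allow gaps from 9 - 3 = 6 to 14 - 1 = 13 months, so raw changes are not on a common time base. The Section 9.6.2 formula counts from diagnosis and is a different quantity. Other measures, such as King's stage or gastrostomy yes/no, need a scale that suits them.
3. If an SMD is kept, make it between groups with one stated common standardiser; the pooled baseline SD is one option.
4. Describe the results as associations with genotype.

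The cost is minor rewording in two places and slightly more analysis, using data the registry already collects.

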### 9.6.2. ALS progression rate

The ALS progression rate ( $\Delta$ ALS-FRS) can be derived from the ALS-FRS. The loss of ALS-FRS value per month, or delta ALS-FRS, indicates the rate of deterioration and predicts survival (Kimura et al. 2006).  $\Delta$ ALS-FRS is calculated using the following formula:

$$\Delta\text{ALS-FRS} = \frac{(48-\text{ALSFRSR})}{\text{Duration of disease since diagnosis (months)}}$$

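### Follow-up change is analysed in complete cases only, although the plan expects loss through progression and death; decline is probably understated and genotype differences in change may be biased

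*Combined protocol and SAP*

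**What the plan says.** Section 11 states: "The analysis of follow-up data is limited to complete" cases, because "not all patients are expected to complete end-of-study assessments due to disease progression, e.g., death". It adds that "missing data records will be omitted and treated as missing values". The effect measure needs a later assessment: "The SMD of each measure over up to 12 months will be estimated using the change in measure" between each subject's assessments. The same section applies its tests to changes over time between genetic subsets.

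Two safeguards are planned. One is to "compare the baseline characteristics and the proportion of death between those who completed and not those not completed 6 months and 12-month assessment". The other is adjustment: "Results of the longitudinal observations will be also controlled for the influence of any covariate (sex, age, intervention history"), plus linear regression on unlisted potential confounders and an unspecified multivariate analysis.

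On completion, section 4.1 plans for approximately 1,000 completers and section 5.1 expects more than 1,000 of 2,000. Section 9.6.2 says the ALS-FRS loss per month "indicates the rate of deterioration and predicts survival". Section 3.3 makes it an objective to compare "functional deficits, disease progression and health care measures in a subset of ALS patients with pathogenic variants" in SOD1 or C9orf72 with patients carrying no mutation in the tested genes.

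**The concern.** The plan removes patients for a reason it names as progression, then estimates progression in those who remain. If faster decliners are more likely to be lost, the completers' mean change understates the cohort's. If carriers and mutation-negative patients have different slopes, the faster group is trimmed more, and a true difference shrinks. If retention differs by genotype for other reasons, a difference of either sign can appear where none exists.

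The completer comparison can reveal selective loss, but it feeds no estimate and is not planned by genotype. Sex and age are not measures of severity, and intervention history is at most a proxy. The adjusted models use the same complete cases. Nor is a complete case defined. It could mean per visit, so that a patient with visits 1 and 2 counts at 6 months, or all three visits.

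**Working it through.** **The plan's own figure.** 1,000 / 2,000 = 50% completion at 12 months. Section 5.1 makes this a floor. No derivation is given and the causes of loss are not apportioned.

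**A check by hand.** Let r be the completion fraction and k the ratio of mean decline in non-completers to that in completers. Then completers' mean / cohort mean = 1 / (r + (1 - r)k). At r = 0.5:
- k = 1.25: 1 / 1.125 = 0.89
- k = 1.5: 1 / 1.25 = 0.80
- k = 2: 1 / 1.5 = 0.67
- k = 1: no bias

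**Illustration with explicit inputs, all assumed.** Gamma-distributed slopes, mean 0.8 points/month in the reference group and 1.1 in carriers, coefficient of variation 0.7; visits at 0, 6 and 12 months; no floor on scores. The probability of loss in each 6 months is logistic in true slope, with coefficient 0.6 (weak), 1.2 (moderate) or 2.0 (strong) per point/month. The intercept is set to give the stated 12-month completion in the reference group. The true genotype difference at 12 months is -(1.1 - 0.8) x 12 = -3.6, and at 6 months -1.8. The 6-month results read complete case as per visit.

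| Weak / moderate / strong | 50% complete | 80% complete |
|---|---|---|
| Reference decline understated, 12 months | 13.2 / 23.3 / 32.1% | 5.6 / 11.3 / 16.9% |
| Reference decline understated, 6 months | 7.3 / 14.3 / 21.8% | 3.0 / 6.5 / 10.8% |
| 12-month difference (true -3.6) | -2.37 / -1.58 / -1.05 | -2.94 / -2.24 / -1.67 |

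At 50% completion the 6-month difference (true -1.8) becomes -1.43 / -1.08 / -0.78.

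The shrinkage can be traced for the weak case at 50%. Reference decline is 0.8 x 12 = 9.6 points, and completers show 9.6 x (1 - 0.132) = 8.33. Carriers truly lose 1.1 x 12 = 13.2, and their completers show 8.33 + 2.37 = 10.70, an understatement of 19% against 13%. Under the same dropout rule, carriers complete 45 / 42 / 39%.

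**No true difference, unequal retention.** With carriers completing 60% against 50%, the spurious 12-month difference is -0.24 / -0.36 / -0.45. At 40% against 50% it is +0.25 / +0.36 / +0.43.

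**Patients alive at the visit.** Give death and other loss the same hazard, with 50% completing overall. The understatement is then 6.9 / 10.9 / 12.8% at 12 months and 3.9 / 7.2 / 9.7% at 6 months. At 80% completion it is 2.8 / 5.2 / 6.6% and 1.5 / 3.2 / 4.7%.

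**Does covariate adjustment help?** With a covariate correlated 0.5 with decline, the 12-month difference at 50% completion is -2.49 / -1.71 / -1.16, against -2.37 / -1.58 / -1.05 without it.

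**Does a mixed model help?** Random intercept and slope, 50% completion, baseline mean 36 and SD 7, measurement SD 1.5 (assumed):
- If loss depends on true slope, reference decline is understated by 8 / 16 / 25% and the 12-month difference is -2.8 / -2.1 / -1.5. At 6 months the difference is -1.4 / -1.0 / -0.7, no better than per-visit complete cases.
- If loss depends on recorded scores, reference decline is within 0.2% of the truth and the 12-month difference is -3.5 / -3.5 / -3.4. Complete cases under that mechanism understate by 8 / 14 / 21% and give -2.9 / -2.2 / -1.7.

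**Group sizes.** Section 2.1 gives SOD1 in 14.8% of fALS and 1.2% of sALS, and C9orf72 in 34% and 5%. With an assumed fALS share f of 5% to 10%:
- SOD1: 2,000 x (0.148f + 0.012(1 - f)) = 38 to 51
- C9orf72: 2,000 x (0.34f + 0.05(1 - f)) = 129 to 158. The 6.5% overall share in section 2.1 gives 130.

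At 50% completion that leaves 19 to 26 SOD1 completers. At the 39 to 45% carrier completion above, it leaves about 15 to 23.

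**The case against.** **Remote capture.** Sections 8.1, 8.2 and 9.6.1 allow ALS-FRS by remote self-assessment, so patients too disabled to attend may still supply it. That weakens the link between progression and missing data. However, the expectation of about 1,000 completers comes from a plan that already includes remote capture, and section 11 still names progression and death as the reason for loss.

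**Estimand.** Understatement relative to everyone enrolled projects a score for patients who have died. This point stands. For patients alive at the visit the figures are roughly half as large or less, and nil if all loss is death.

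**Size.** 50% is a floor, and at 80% the alive-at-visit understatement is only 1.5% to 6.6%. The spurious differences of 0.2 to 0.45 points are small beside a standard error of about 0.9 to 1.4 points for the mean 12-month change in 19 to 26 SOD1 completers. Both points are fair. The shrinkage of a true difference, by 1.2 to 2.5 points at 50% completion, is not small.

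**The remedy is partial.** This is true if loss depends on unrecorded decline.

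**Vague wording leaves room.** Baseline severity could be among the unlisted confounders. That would help only so far as it predicts decline, and the analysis would still discard patients seen at visit 2 but not visit 3 from the 12-month comparison.

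**Exploratory status.** Section 3.4.2 says no hypothesis is tested, and the limitation is openly stated. That lowers the priority. Section 11 nevertheless plans p-values at 5% and confidence intervals for these comparisons.

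**Conclusion.** The concern holds and should be fixed. As written, the plan probably understates decline from visit 1 to visits 2 and 3 for the enrolled cohort and can bias genotype differences in change, with nothing planned that corrects either. The existence of the problem follows from the plan's own text. Its size does not, because every slope and dropout input above is assumed. At 50% completion the illustrated 12-month understatement is 13% to 32% for the enrolled cohort and 7% to 13% for patients alive at the visit. A true difference of -3.6 shrinks to between -2.4 and -1.1 if both groups follow the same dropout rule. If loss is unrelated to decline there is no bias. The direction of the genotype bias cannot be fixed from the documents, because retention may differ between groups. The primary endpoint, the baseline comparisons and the visit 1 progression rate are untouched.

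**What to change.** 1. Make the main analysis of ALS-FRS change (and of MYMOP where repeated) a linear mixed model on all observed scheduled visit 1 to 3 values, with actual months since visit 1 and a genotype-by-time term. Patients with visits 1 and 2 only then contribute to the 12-month comparison.
2. State the estimand. This model describes the trajectory as if nobody dropped out, and so implicitly extends it past death. Say that it relies on loss depending on recorded data.
3. Report deaths and other losses by genotype at visits 2 and 3. Add time to death from enrolment by genotype (Kaplan-Meier and Cox) from the date-of-death field in Table 4.
4. Keep the completer comparison, and add it by genotype. Keep complete cases as a sensitivity analysis, defined as per visit or all three visits.
5. Table 1 marks King's stage, PEG and ventilation at visits 1 and 3 only, so the model adds nothing there. Report numbers observed, lost and dead by genotype.

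The cost is SAP wording and modest programming with standard procedures. The one new data item is a vital-status check at closure, since Table 1 lists date of death but marks it at no visit. Data erased on withdrawal of consent (section 12.7) cannot be used. Where loss depends on unrecorded decline, the gain is partial at 12 months and nil at 6 months against per-visit complete cases.
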